Neoadjuvant endocrine therapy is a safe and effective strategy for treatment and response assessment in both pre- and postmenopausal women with HR+ HER2 negative disease. Most of the randomized clinical trials comparing different endocrine agents in neoadjuvant setting have involved patients with locally advanced breast cancer (LABC) and the duration of treatment has ranged anywhere from two weeks to four months, with responses as early as 10 to 14 days. Aromatase inhibitors have shown increased efficacy compared with tamoxifen in postmenopausal breast cancer patients, whereas tamoxifen alone or with ovarian function suppression are standard treatment options for premenopausal women with HR+ breast cancer.⁶ The P024 trial showed that neoadjuvant treatment with letrozole is superior to tamoxifen in terms of clinical response rate (55% versus 36%, $P = 0.001$) and breast conservation rate (45% versus 35%, $P = 0.022$) in postmenopausal women with LABC.⁷ The IMPACT trial treated 330 postmenopausal women with LABC with anastrozole, tamoxifen or a combination of tamoxifen and anastrozole for 12 weeks before breast surgery and found no significant differences in objective response rates between the three arms (37%, 36%, and 39% respectively, $p=0.23$).⁸ The STAGE trial showed improved objective response rates, in addition to increased rates of breast conservation surgery in premenopausal women with 24 weeks of neoadjuvant anastrozole, combined with goserelin, as compared with tamoxifen combined with goserelin.⁹ ACOSOG-Z1031 showed no significant difference in clinical responses or surgical outcomes between the three commonly used aromatase inhibitors, exemestane, letrozole and anastrozole, in postmenopausal women.¹⁰

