 - Partial Response (PR):** A 50% or greater decrease in the product of the bidimensional measurements of the lesion (total tumor size), based on a comparison between the measurements at baseline and after four weeks of treatment with neoadjuvant therapy.
 - No Change (NC):** A 50% decrease in total tumor size cannot be established nor has a 25% increase in the size of the lesion been demonstrated.
 - Progressive Disease (PD):** A 25% or greater increase in the total tumor size of the measurable lesions (calculated on the smallest diameter recorded over time).

V. STUDY ENTRY AND WITHDRAWAL; STUDY PROCEDURES

Required Preregistration Screening Tests and Procedures

The study-specific assessments are detailed in this section and are outlined in the study calendar. Screening assessments must be performed within 28 days prior to enrollment. Any results falling outside of the reference ranges may be repeated at the investigator's discretion. Treatment or visit delays for public holidays or weather conditions do not constitute a protocol violation.

A written, signed informed consent form (ICF) and a Health Insurance Portability and Accountability Act (HIPAA) authorization must be obtained before any study-specific assessments are initiated. A separate consent form for tissue banking of residual tumor specimens would be used. Signed copies of the study consent forms would be given to the subject. and a copy will be filed in the medical record. The original study consent will be kept on file with the study records.

All patients who are consented will be registered in OnCore®, the MCW Cancer Center clinical trial management system. The system is password protected and meets HIPAA requirements.

Registration Procedures

Registration and Monitoring of Patients

1. Patients will be screened for eligibility and registered by a certified research associate/certified research coordinator (CRC/CRA) in the Clinical Trials Office of the Froedtert & the Medical College of Wisconsin Clinical Cancer Center.
2. Patients will be registered in the institutional OnCore® web-based system under the CRA console.

3. Registration of patients and information regarding consenting, eligibility review, on-study status, treatment status and follow-up will be monitored, using the OnCore® calendar system.
4. Serious adverse events (SAEs) and protocol deviations will be reported through the OnCore® reporting system.

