5. Other less commonly reported side effects are anti-estrogen symptoms, i.e., hot flashes, mood changes and weight changes. Some of the rare but serious side effects, such as ischemic cardiovascular event, thromboembolic event or uterine cancer with tamoxifen are long-term side effects and are not expected to occur during this short course of neoadjuvant treatment. Similarly, decrease in bone density with aromatase inhibitors is a slow and long-term side effect, not expected to be seen during the four-week study period.
6. There are no dose modifications or reductions recommended with endocrine treatment.

VII. STATISTICAL CONSIDERATIONS

Statistical analyses:

Demographic and baseline characteristics, such as age, race, weight, values of all biomarkers pre and post-treatment, response measures will be summarized, using means, standard deviations, medians, ranges for continuous variables, and proportions for categorical variables.

This is an exploratory study to gather information on how frequently protein levels of HER growth factor receptors (HER1-4) are upregulated along with changes in other study biomarkers and correlation with Ki-67 in response to short-term neoadjuvant endocrine in early stage HR+ breast cancer. We hypothesize that expression of one or more HER proteins (HER1-4) will be upregulated in at least 50% of tumors after four weeks of neoadjuvant endocrine therapy and this upregulation will correlate with Ki-67 expressed in more than 10% of cancer cells, as compared to upregulation in 30% or less of tumors without the therapy. The change in Ki-67 expression will be dichotomized, as a categorical variable with $\geq 10\%$ increase coded as high and $< 10\%$ coded as low.

- a) For the primary outcome: An exact binomial one sample test of proportions will be used for to test the hypothesis that proportion of upregulated HER proteins will be at least 50% after therapy versus the null hypothesis that the proportion of upregulated HER proteins is not greater than 30%.
- b) For analyzing - the differences in proportion of upregulated HER proteins between the high difference in Ki-67 and low difference in Ki-67 groups, two sample tests of proportions will be used.

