- c) Similarly, appropriate two sample tests will be used to test differences in biomarkers between the high difference in Ki-67 and low difference in Ki-67 groups. We will use the appropriate kind of regression instead of two sample tests, to test differences in biomarkers between the high difference in Ki-67 and low

difference in Ki-67 groups if we need to adjust for covariates.

- d) Additionally, regression analysis will also be done to evaluate the changes in the biomarkers and their association with patient specific covariates, such as age, race and other relevant predictors of interest.

Radiographic responses will be assessed by WHO criteria. Radiographic response rates will be measured as the rate of complete response (CR) or partial response (PR) in patients treated with neoadjuvant endocrine therapy. Complete response is defined as the resolution of tumor on post-treatment imaging as compared with pretreatment imaging, while partial response is defined as 50% reduction in tumor size on post-treatment imaging, as compared with pretreatment imaging. We will estimate the rates of response with 95% confidence intervals. We will use logistic regression (and other generalized linear models as appropriate) to measure association between the response rates and patient specific covariates such as age, race and other relevant predictors of interest.

We will use a family type I error rate of 0.05 significance throughout with Bonferroni adjustments for multiple testing wherever appropriate, so that the overall family type I error rate is maintained.

Sample Size and Power Calculation

To achieve at least 80% power at significance level of 0.05, when testing the one sided one sample hypothesis that the proportion of tumors with HER protein upregulation with neoadjuvant endocrine therapy is at least 50% versus the null hypothesis that the proportion is no larger than 30%, **the minimum number of patients required is 37.**

Early Stopping for Futility

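### The logistic regression of radiographic response on age, race and other predictors has no sparse-data method; if the response rate is about 10% or lower, fits that include race will often have no finite estimate

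*Combined protocol and SAP*

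**What the plan says.** Section VII (Statistical analyses) makes CR or PR by WHO criteria a binary outcome and estimates its rate with a 95% confidence interval. It then continues: "We will use logistic regression (and other generalized linear models as appropriate) to measure association between the response rates and patient specific covariates". The covariates named are age and race, followed by an open-ended reference to other predictors. The section gives no expected CR/PR rate, no limit on the number of predictors, and no penalised or exact method for few events or an empty cell.

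Section IV (Definitions of Radiographic Responses) defines partial response as "A 50% or greater decrease in the product of the bidimensional measurements of the lesion". Treatment lasts four weeks, plus or minus one week, in clinical stage I or II disease.

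The sample size belongs to another endpoint. Section VII (Sample Size and Power Calculation) says "the minimum number of patients required is 37", and that number is for the test of HER protein upregulation.

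Section I (Advantages of the Neoadjuvant Treatment Approach) cites response rates from two trials in locally advanced disease. A letrozole versus tamoxifen trial had 55% versus 36%, with no treatment duration given. A 12-week, three-arm trial "found no significant differences in objective response rates between the three arms", at 37%, 36% and 39%. The same section says responses can appear as early as 10 to 14 days, but attaches no rate to that statement.

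**The concern.** A logistic model fitted by ordinary maximum likelihood has no finite estimate when a covariate, or a combination of covariates, separates responders from non-responders. With a binary covariate this happens as soon as one of the four covariate-by-response cells is empty. With 37 patients, a race minority of a handful and few responders, an empty cell is easy to get. Moving to another generalised linear model, as the plan allows, does not in itself cure this.

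When the fit does converge in a sample this small, the coefficients are on average too far from zero.

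Section I expects the study to identify predictors of responsiveness. An undefined or exaggerated odds ratio would undercut that aim. It would also push the team into choosing a method or dropping a covariate after seeing the data.

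**Working it through.** **The plan's own figure.** No figure is stated for CR/PR or for the regression. The only sample-size figure is 37, for HER upregulation (30% versus 50%, one-sided 0.05, 80% power). The arcsine formula reproduces it: ((1.645 + 0.842) / (2 asin √0.5 − 2 asin √0.3))² = 36.51, so 37. It carries no information about the number of radiographic responders. (The planned exact binomial test at 37 rejects at 17 or more, with power 0.744. That is a separate matter and does not affect this point.)

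**Inputs from the documents.** n = 37; binary outcome CR/PR; covariates age, race and others; cited rates 36% to 55%.

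**Assumptions, because the documents are silent.** A grid of response rates; race as binary with 4, 6 or 11 of 37 in the smaller group; one further binary predictor with 11 of 37; no true covariate effects unless stated.

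**Step 1: the threshold.** If both diameters shrink equally, a 50% fall in their product means each falls to √0.5 = 0.707 of baseline, a 29.3% reduction. This is less strict than halving a diameter.

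**Step 2: expected responders, 37 × rate.** 1.9 at 5%, 3.7 at 10%, 7.4 at 20%, 13.3 at 36%, 20.4 at 55%. The probability of no responder at all is 0.95³⁷ = 0.15 at 5% and 0.9³⁷ = 0.02 at 10%.

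**Step 3: race alone, exact.** With m in the smaller group, k = 37 − m, response rate p and q = 1 − p:

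P(no finite estimate) = 1 − (1 − qᵐ − pᵐ)(1 − qᵏ − pᵏ).

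For m = 6, k = 31, p = 0.10 this is 1 − (1 − 0.5314)(1 − 0.0382) = 0.55. Section V mentions an accrual goal of 39. With k = 33 the second bracket becomes 1 − 0.0309 and the result is still 0.55.

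**Step 4: models with age.** 1,500 simulated data sets per cell, with complete or quasi-complete separation detected by linear programming. The simulation error is at most √(0.25/1500) = 0.013.

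Probability of no finite estimate, by assumed CR/PR rate:

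| Predictors | 5% | 10% | 20% | 36% | 55% |
|---|---|---|---|---|---|
| Age only | 0.18 | 0.03 | 0.00 | 0.00 | 0.00 |
| Race only, 6 v 31 (exact) | 0.79 | 0.55 | 0.26 | 0.07 | 0.04 |
| Age + race, 4 v 33 | 0.86 | 0.67 | 0.41 | 0.20 | 0.12 |
| Age + race, 6 v 31 | 0.81 | 0.56 | 0.26 | 0.06 | 0.03 |
| Age + race, 11 v 26 | 0.69 | 0.36 | 0.08 | 0.01 | 0.00 |
| Age + race (6) + one more binary (11) | 0.86 | 0.68 | 0.32 | 0.08 | 0.04 |

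A second simulation used a true age effect (log odds ratio 0.70 per SD) and a 20% race minority. The age-plus-race fit failed in about 77%, 53%, 21% and 6% of trials at response rates of 5%, 10%, 20% and 35%.

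**Step 5: bias when the fit is finite.** With the same true value of 0.70 and a 35% response rate, the maximum-likelihood age coefficient averaged 0.79 to 0.82, that is 0.79/0.70 = 1.13 to 0.82/0.70 = 1.17 times the truth. Adding a third covariate gave 0.84 (1.20 times). Firth-penalised estimates averaged 0.71. At 5% response the Firth average was 0.59 in one run and no lower than 0.67 in another, so some shrinkage appears when responders are very few.

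**The case against.** A reader might infer that the trial will have few responders and that the planned model will therefore usually fail. The documents do not support that. They state no CR/PR rate at three to five weeks, and their cited rates would give about 13 to 20 responders, where failure is 0% to 20%. The note that responses appear within 10 to 14 days also points away from certainty that they will be rare. Nor can the cited rates be dismissed as the product of many months of treatment: 12 weeks is stated for one trial and no duration for the other. What stands is that both trials were in locally advanced disease, and that section I (Future Directions) itself concedes there may not be enough responses for statistical significance.

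A reader might also take the plan to specify a joint model with Wald intervals. It specifies neither, and fitting one covariate at a time is already compatible with it. That only partly helps: age alone is then safe at rates of 10% or more, but race alone still fails with probability 0.55 at 10% (6 v 31).

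The size of the bias needs care. It is an average pulled up by a skewed tail. In an age-only model the maximum-likelihood mean was 0.78 to 0.84 but the median 0.68 to 0.75, against 0.70. The means also compare finite maximum-likelihood fits with Firth fits from every trial that has a responder, which is not quite like for like.

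Finally, this is a covariate analysis of a secondary endpoint in an exploratory study. The response rate and its 95% interval are unaffected, and separation is visible when it occurs. All of that stands and limits the weight of the point.

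**Conclusion.** The concern holds in conditional form, as a low-cost improvement to a secondary analysis. With a race minority of about 20%, an ordinary maximum-likelihood fit including race has no finite estimate in roughly half or more of trials if the CR/PR rate is about 10% or lower, and in about one in five to one in four at 20%. At the cited rates it seldom fails. Balance matters: with 11 of 37 in the smaller group, the figure at 10% falls to 0.36.

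The average inflation of about 10% to 20% remains at 35% response, close to the lowest cited rate, and Firth penalisation largely removes it there. The response-rate grid, the race split, the extra predictor and the age effect are all assumptions. Stronger covariate effects or more race categories would generally raise the failure rate.

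**What to change.** In section VII (Statistical analyses), and in the matching sentence of the Protocol Summary, replace ordinary logistic regression of CR/PR with Firth-penalised logistic regression and profile-likelihood 95% confidence intervals. State that covariates will be fitted one at a time when responders are few, and that the results are descriptive. If there are no responders, report only the rate and its interval.

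The team should define few before the response data are seen. A round number such as 10 responders may be tempting, but neither the documents nor these calculations support a particular cut-off.

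The cost is a sentence or two of SAP wording, with no added patients, visits or data. The downside is little or no mutual adjustment between covariates, and slight shrinkage of estimates when responders are very few.

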Institute for Health and Society
Division of Biostatistics
[name]
[name]
[contact]
[contact]

PROTOCOL SUMMARY

[figure not shown]
Title	An Exploratory Study of Neoadjuvant Endocrine Therapy in Hormone Receptor-Positive HER2-negative Node-Negative Breast Cancer Patients to Assess Responses and Mechanisms of Endocrine Resistance
Protocol Number	FP00011093; PRO 30178.
IND Sponsor	N/A
Principal Investigator	[name], MS
Study Sites	St. Joseph's Hospital, West Bend Community Memorial Hospital, [name] Memorial Lutheran Hospital
Clinical Trial Phase	Exploratory
Study Disease	Hormone receptor-positive (HR+), HER2-negative (Her2-), node-negative pre and postmenopausal breast cancer patients.
Study Rationale	Patients with HR+ HER2- node-negative breast cancers generally undergo surgical resection upfront, followed by adjuvant chemotherapy, if needed, in addition to adjuvant endocrine therapy. Because endocrine therapy is primarily delivered in the postoperative setting, the ability to assess the tumor response to this treatment modality is lost and very difficult to assess. This study offers the unique opportunity to assess the responsiveness of breast tumors to endocrine therapy while the tumors are still in vivo by treating patients with endocrine therapy before surgery and assessing molecular changes with treatment. By comparing pre- and post-treatment levels of molecular markers in individual tumors, we expect to identify predictors of responsiveness to existing agents and identify new candidate therapeutic targets.
Primary Objectives	Our primary objective is to determine the frequency of increased HER family of receptor tyrosine kinases protein expression in tumors, following treatment with neoadjuvant endocrine therapy and their correlation with Ki-67 tumor responses. We will measure cancer cell protein levels of growth factor receptors of the HER family before and after neoadjuvant endocrine therapy. The data will be used to inform a future randomized trial of combined endocrine and the most promising anti-HER targeted therapy.
Secondary Objectives	
 - To determine changes in additional selected molecular markers (CK5+/ER- progenitor cells, PD-L1, PD-L2, BTK, iron-related proteins) and correlate with Ki-67 responsiveness to endocrine therapy in our pre- and post-treatment tumor specimens.

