The following objectives are designed to test these hypotheses:

Primary Objective

Determine the frequency of increased **HER-protein expression** in tumors following treatment with neoadjuvant endocrine therapy and their association with tumor Ki-67 expression. We will measure cancer cell protein levels of growth factor receptors of the HER family before and after neoadjuvant endocrine therapy. The data will be used to inform a future randomized trial utilizing a combination of endocrine treatment and the most promising anti-HER targeted therapy.

Secondary Objectives and Associative Studies

Our secondary objectives are focused on other biomarkers and pathways of interest. Our goal is to determine changes in gene expression and/or protein levels of the following biomarkers with neoadjuvant endocrine therapy and correlation with tumor responses.

1. Determine whether an increased proportion of **therapy-resistant CK5+ progenitor cells** are negatively correlated with a response in Ki-67 and tumor volume reduction, in response to neoadjuvant endocrine therapy.
2. Assess changes in the **% expression of ER and PR** in pre- and post-treatment breast cancer tumor specimens and their correlations with Ki-67 and radiographic responses.
3. Assess changes in **BTK protein expression** with neoadjuvant endocrine therapy and correlation with responses.
4. Changes in **iron-related protein expression, i.e., transferrin, ferritin, ferroportin and ribonucleotide reductase** with neoadjuvant endocrine therapy and correlation with responses.
5. Changes in PD-L1 and PD-L2 protein expression with neoadjuvant endocrine therapy.

6. Assess changes in tumor size on radiographic images with neoadjuvant endocrine therapy and correlate with changes in biomarkers and Ki-67.
7. Chart review planned at about five years from completion of study to assess patient outcomes, i.e., ipsilateral, contralateral or distant recurrences.

III. ELIGIBILITY CRITERIA

Inclusion Criteria

1. Unilateral diagnostic breast mammogram and ultrasound within 60 days of enrollment.
2. Pathologically proven diagnosis of invasive breast cancer, clinical stage I or II.
3. Patients must be clinically lymph node negative. Lymph node negativity must be confirmed by clinical exam and/or ultrasound imaging.
4. The patient must be female.
5. Age ≥ 18 years.

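### Holm's step-down adjustment would keep the planned 0.05 family error rate for the secondary markers and never reject less than Bonferroni; the gain is modest

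*Combined protocol and SAP*

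**What the plan says.** Section VII (Statistical analyses) ends with the multiplicity rule: "We will use a family type I error rate of 0.05 significance throughout with Bonferroni adjustments for multiple testing wherever appropriate", with the stated purpose "so that the overall family type I error rate is maintained". The section names no other procedure. It does not list a family, count the tests, or say which comparisons are adjusted.

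The comparisons most likely to need adjustment are in item c of the same section: "appropriate two sample tests will be used to test differences in biomarkers between the high difference in Ki-67 and low difference in Ki-67 groups". The grouping comes from Ki-67: "The change in Ki-67 expression will be dichotomized, as a categorical variable", with an increase of at least 10% coded as high. Group sizes are not projected.

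The marker list is in Section II (Secondary Objectives and Associative Studies), which opens: "Our secondary objectives are focused on other biomarkers and pathways of interest". It covers CK5+ progenitor cells, "expression of ER and PR", BTK, the iron-related proteins ("transferrin, ferritin, ferroportin and ribonucleotide reductase"), PD-L1 and PD-L2. That is 1 + 2 + 1 + 4 + 2 = 10 markers.

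**The concern.** The plan wants the family error rate held at 0.05. Bonferroni does this with one fixed threshold for every test. Holm gives the same guarantee with thresholds that relax after each rejection. A procedure that meets the same guarantee and can only reject more is preferable unless something else is lost.

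At stake are the second and later markers. The background section on future directions would use the marker results to choose patients for follow-up trials of several drug classes, so each further marker has some value. The same section concedes that significance may be missed at this sample size.

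**Working it through.** **The plan's own figure.** The plan states no threshold or power for the marker tests. Its only sample-size figure is 37, for the primary test (30% against 50%, one-sided 0.05, 80% power). The arcsine approximation reproduces it: h = 2·arcsin√0.50 − 2·arcsin√0.30 = 0.4115, and n = ((1.645 + 0.842)/0.4115)² = 36.5, rounded up to 37. Below, 37 serves only as the total number of patients.

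**Inputs.**
- From the plan: family rate 0.05, 37 patients, the ten listed markers, two Ki-67 groups.
- Assumed, because the plan gives no value: all ten markers form one family; two-sided tests; marker correlation 0 or 0.3; group sizes; effect sizes; number of true markers.

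**Thresholds for m = 10.** Bonferroni compares every p-value with 0.05/10 = 0.0050. Holm orders the p-values and compares them in turn with 0.05/10, 0.05/9, …, 0.05/1, stopping at the first failure: 0.0050, 0.0056, 0.0063, 0.0071, 0.0083, 0.0100, 0.0125, 0.0167, 0.025, 0.05.

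**Why Holm never rejects less.** No Holm threshold is below 0.05/m, so any p-value that passes Bonferroni also passes Holm. The simulations found no exception.

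**Why the error rate holds.** Suppose m₀ null hypotheses are true. The first false rejection can come no later than step m − m₀ + 1, where the threshold is 0.05/m₀. The family error is then at most m₀ × 0.05/m₀ = 0.05, whatever the dependence.

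**Size of the gain, normal test statistics** (ten markers, correlation 0.3, mean z = 3 for true markers). Bonferroni power per true marker is about 57 to 58%. As a check, the two-sided 0.005 critical value is 2.807, and Φ(3 − 2.807) = Φ(0.193) ≈ 0.577.

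| True markers of 10 | Gain in average power with Holm (points) |
|---|---|
| 1 | 0.1 |
| 3 | 1.6 |
| 5 | 3.4 |
| 8 | 7.6 |

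The chance of finding at least one true marker is the same under both methods (86.2% with three true, 93.5% with five), because the first Holm step is the Bonferroni threshold.

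**Effect of the split.** For a 1-SD difference, mean z ≈ √(n₁n₂/37). An 18/19 split gives √(342/37) = 3.04, a 9/28 split gives √(252/37) = 2.61, and a 4/33 split gives √(132/37) = 1.89. At 9/28 the gain is 1.3 points with three true markers and 2.8 with five. At 4/33 it is about 0.6 and 1.1.

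**Simulated two-sample t tests** (ten markers, 1.0 SD, correlation 0.3, 10,000 runs each). Base power is lower than above because the SD is estimated.

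| Split | True markers | Average power, Bonferroni / Holm | At least one found, Bonferroni / Holm |
|---|---|---|---|
| 18/19 | 1 | 51.7% / 51.8% | 51.7% / 51.8% |
| 18/19 | 5 | 52.6% / 56.4% | 91.8% / 91.9% |
| 18/19 | 10 | 52.4% / 65.4% | 97.4% / 97.4% |
| 9/28 | 1 | 36.5% / 36.5% | 36.5% / 36.5% |
| 9/28 | 5 | 36.6% / 39.3% | 79.3% / 79.4% |
| 9/28 | 10 | 37.1% / 46.5% | 91.5% / 91.5% |

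Over differences of 0.8 to 1.2 SD and both splits, the ten-marker gain is at most 0.1 points with one true marker, about 1 to 4 with five, and about 2.5 to 16 with all ten true.

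**Realised family error** (normal statistics, z = 3). With five true markers it is 2.4% for Bonferroni and 3.5% for Holm; with eight it is 1.0% and 2.8%. The Bonferroni values agree with its bound m₀ × 0.005: 5 × 0.005 = 0.025 and 2 × 0.005 = 0.010.

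**The case against.** Bonferroni is valid, conservative and prespecified, and the study is declared exploratory. Nothing in the plan says that a marker failing the adjusted test is discarded, and Section VII summarises all biomarkers before and after treatment. The benefit of Holm is close to nil if only one marker is real, and the chance of finding at least one candidate does not change. An even Ki-67 split is also doubtful: the high group needs an increase in Ki-67, while the background section on Ki-67 describes reductions under this treatment. All of this stands, and it limits the point to an efficiency suggestion.

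A reader might infer that the plan commits the ten secondary markers to a 0.005 threshold each. The text does not say so. The adjustment applies only where appropriate, no family is defined, and the markers are separate numbered objectives, so smaller families are an equally fair reading.

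A reader might also take the fall in power for a 1-SD difference in an 18/19 split, from 84.0% at 0.05 to 52.5% at 0.005, as what Holm would recover. That contrast is the cost of adjusting at all. Holm starts at the same 0.005 and recovers only part of the loss, for markers after the first.

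Nor does Bonferroni give up power for nothing. It supplies matching simultaneous confidence intervals directly and has a lower realised family error. Both advantages are small here: the only intervals the plan requests are for radiographic response rates, and Holm stays within the plan's own 0.05 limit. The objection leaves the dominance result untouched.

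**Conclusion.** The point holds as a low-priority improvement. It rests on a mathematical fact that needs no assumption about effects: Holm meets the plan's stated error target and rejects everything Bonferroni rejects. The size of the gain does rest on assumptions about family size, correlation, effects and group split, none of which the documents supply. Under the ten-marker assumption it is roughly 0 to 4 points of average power per true marker unless most of the markers are truly associated with Ki-67 change. The undefined family is the larger gap in the same sentence, since no adjustment can be applied reproducibly until its members are listed.

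**What to change.** In Section VII, for the comparisons of secondary markers between the Ki-67 groups, replace the Bonferroni wording with a Holm step-down adjustment at a family rate of 0.05. List the members of the family there, for example CK5+/ER- cells, ER, PR, BTK, the four iron-related proteins, PD-L1 and PD-L2. Report Holm-adjusted p-values. If confidence intervals are given for markers, label them as unadjusted 95% or Bonferroni-level, because they will not match Holm decisions exactly.

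The cost is a sentence or two of text and a decision on the marker list. It needs no extra patients, tissue, visits or assays.
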